Description of Study Intervention/Procedure	A 10-week exercise program with both aerobic and resistance components, based on the American College of Sports Medicine (2010), will be individually prescribed to 40 DPN patients. Prior to beginning the intervention, subjects will participate in a maximal graded exercise test (VO 2 R) using a cycle ergometer with a metabolic cart and integrated ECG.
Reference Therapy	N/A
Key Procedures	Oral Glucose Tolerance Test (OGTT), multinuclear-MRI, VO 2 R, MNSI, physical therapy, activity monitor

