# 1.3 Potential Risks & Benefits

# 1.3.1 Known Potential Risks

There are two categories of risk associated with this study:

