- RPE will be assessed at baseline and every 20 minutes. A moderate RPE level (11–13 on the 17point scale) should be achieved at each session.

Adverse event tracking: Adverse events will be tracked at each session. Events will be classified as related to exercise intervention or unrelated to exercise intervention. Severity will be classified using the Common Terminology Criteria for Adverse Events (CTCAE) v5.0. [name]. will serve as the safety monitor for this study and review adverse events as necessary.

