# 6.6 Prohibited Medications, Treatments, and Procedures

Oral medications such as Metformin are prohibited two full days prior to all OGTT evaluations. Participants will be asked not to take their insulin on the morning of their visit at CBI.

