# 7.1.3 Definition of Unanticipated Problems (UP)

### **Unanticipated Problems Involving Risk to Subjects or Others**

Any incident, experience, or outcome that meets all of the following criteria:

- Unexpected in nature, severity, or frequency (i.e. not described in study-related documents such as the IRB-approved protocol or consent form, the investigators brochure, etc.)
- Related or possibly related to participation in the research (i.e. possibly related means there is a reasonable possibility that the incident experience, or outcome may have been caused by the procedures involved in the research)
- Suggests that the research places subjects or others at greater risk of harm (including physical, psychological, economic, or social harm).

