## 7.2.2 Relationship to Study Intervention

The clinician's assessment of an AE's relationship to study intervention is part of the documentation process, but it is not a factor in determining what is or is not reported in the study. If there is any doubt as to whether a clinical observation is an AE, the event should be reported. All AEs must have their relationship to study intervention assessed. In a clinical trial, the study intervention must always be suspect. To help assess, the following guidelines are used.

- **Related** The AE is known to occur with the study intervention, there is a reasonable possibility that the study intervention caused the AE, or there is a temporal relationship between the study intervention and event. Reasonable possibility means that there is evidence to suggest a causal relationship between the study intervention and the AE.
- Not Related There is not a reasonable possibility that the administration of the study intervention caused the event, there is no temporal relationship between the study intervention and event onset, or an alternate etiology has been established.

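### The adverse event causality item refers only to the study (exercise) intervention, so harm from study procedures has no place in it and may be misattributed in either direction.

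*Combined protocol and SAP*

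**What the plan says.** **Causality of adverse events.** Section 7.2.2 states the general rule: "All AEs must have their relationship to study intervention assessed". It offers two categories. Related applies if the event is known to occur with the intervention, if causation is reasonably possible, or if there is a temporal relationship. Not Related applies if causation is not reasonably possible, if "there is no temporal relationship between the study intervention and event onset", or if another cause has been established. Section 7.3 makes the same judgement a collected item on the case report form and opens the recording window at informed consent, so events before training are in scope.

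**Training sessions.** The adverse event tracking paragraph closes the exercise-programme text in section 6.4 (printed under the 6.4.2 heading). It says "Adverse events will be tracked at each session" and then "Events will be classified as related to exercise intervention or unrelated to exercise intervention".

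**What the intervention is.** Section 5 describes an exercise programme and nothing else. The Protocol Summary puts the maximal test ahead of it: "Prior to beginning the intervention, subjects will participate in a maximal graded exercise test".

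**Other procedures that the trial imposes.** Section 6.6 says "Oral medications such as Metformin are prohibited two full days prior to all OGTT evaluations", and insulin is held on the morning of the visit. Section 6.2.1 adds a 75 g glucose drink with serial blood draws for the oral glucose tolerance test (OGTT). Section 6.3 describes the MRI session.

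**Listed risks.** Section 1.3.1 says "There are two categories of risk associated with this study" and names physical exercise and MRI. Drug withholding and the OGTT are not among them.

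**Unanticipated problems.** Section 7.1.3 uses a different reference: "Related or possibly related to participation in the research", explained as covering the research procedures. The event must also be unexpected and suggest greater risk.

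**The concern.** A single related / not related item tied to the exercise programme cannot record that a study test caused an event. Drug withholding, the glucose load, the maximal test and the MRI are all imposed by the trial, and all could be changed if they caused harm. The safety officer's cumulative review (section 7.5) and the yearly risk-benefit assessment (section 8) depend on knowing which study component an event came from. If procedure harm is labelled unrelated before training and possibly exercise-related after it, the tables understate harm from the procedures and may overstate harm from the exercise.

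**Working it through.** The plan gives no figure to reproduce. The check sets the causality wording against the calendar.

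**Step 1. Schedule (Attachment A).** Aerobic and resistance exercise run from Week 7 to Week 16.

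| Procedure | Before training | After training |
|---|---|---|
| OGTT with drug withholding | Week 1 | Week 18 |
| MRI | Weeks 1 and 5 | Week 18 |
| Maximal test | Week 6 | Week 17 |
| Total per participant | 1 + 2 + 1 = 4 | 1 + 1 + 1 = 3 |

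All 7 procedures fall outside the training weeks.

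**Step 2. Apply section 7.2.2, taking the intervention to be the exercise programme.**

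- *The four procedures before training.* The event precedes all exercise, so no temporal relationship to it can exist and exercise cannot have caused it. The wording gives Not Related, even when the procedure is plainly the cause.
- *The three procedures after training.* The alternatives under each category are joined by *or*. An event in Week 17 or 18 can count as Related because it follows training closely. It can also count as Not Related if the procedure is accepted as another cause. Neither label names the procedure.

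**Step 3. Scale to 40 participants, all completing the schedule.**

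- Before training: 40 × 4 = 160 procedures.
- After training: 40 × 3 = 120 procedures.
- Total: 160 + 120 = 280.

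The three-MRI count follows sections 1.2 and 3.1 and Attachment A. Sections 9.3.1 and 12.3 give two MRIs, and 9.3.1 places them at enrolment and after the programme. On that count the figures are 40 × (1 + 1 + 1) = 120 before and 40 × 3 = 120 after, 240 in all. These are occasions on which harm could arise. The documents give no event rates.

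**Step 4. Compare with section 7.1.3.** Take marked hyperglycaemia at the Week 1 OGTT after drug withholding. On the adverse event form it is Not Related, because training has not begun. Under section 7.1.3 it is related, because a research procedure may have caused it. That second test becomes an unanticipated problem only if the event is also unexpected and suggests greater risk. A procedure harm that does not meet both conditions keeps only the Not Related label.

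**The case against.** Several points on the other side are sound.

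- **The sentence on exercise relatedness covers training sessions only.** A reader might infer from it that every adverse event in the trial is judged against exercise alone. The general rule is in sections 7.2.2 and 7.3, which refer to the study intervention. Section 7 does not say that study tests are excluded from that term, and the Protocol Summary row that mentions the maximal test is headed as covering both intervention and procedure. A broad reading is therefore possible. Section 5 and the placing of the maximal test before the intervention favour the narrow one. If the broad one was meant, the training-session wording still needs aligning with it.
- **A second relatedness route exists.** Section 7.1.3 covers research procedures, so it would be wrong to say that relatedness is judged only against exercise. The route is limited to events that also meet its other two conditions.
- **Maximal-test events have their own scheme.** Section 1.3.1 sorts test outcomes into Types a, b and c and requires a written report within 48 hours for Types b and c. It documents those events, but it is not a causality item and does not reach the OGTT, drug withholding or MRI.
- **No events are lost.** A reader might infer that procedure harm would be hidden. The documents do not support that. All adverse events are recorded whatever their relationship (7.3), relatedness does not decide what is reported (7.2.2), the duty to report adverse events to the IRB goes by severity (7.4.1), and the safety officer reviews all of them (7.5). A cluster on test days could still be found from event descriptions and onset dates.
- **Expectedness may have other sources.** Consent forms describe study procedures and risks (11.3.1) and are not available here. The omission of drug withholding and the OGTT from section 1.3.1 is a fact. That no risk description exists anywhere cannot be shown.

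**Conclusion.** The point holds as a misattribution problem. The adverse event causality item has no place for procedure-caused harm, and its reference differs from that of section 7.1.3. On the written wording, harm at four procedures per participant (160 across 40) would be labelled Not Related, and harm at three (120 across 40) could be labelled Related to exercise on timing alone. With two MRIs the counts are 120 and 120.

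This rests on reading the study intervention as the exercise programme and on all 40 participants completing the schedule. The adverse event form itself was not available, so its content is taken from section 7.3. The effect is on the cause shown in the safety review and tables. Recording, review and IRB reporting of events are unaffected. How many events would be mislabelled cannot be estimated from the documents.

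**What to change.** In sections 7.2.2 and 7.3 and on the adverse event form, assess relatedness to the exercise training and, as a separate item, to study procedures: the maximal test; drug withholding, OGTT and blood draw; and MRI. Align the training-session tracking paragraph in section 6.4 with this, and make the combined definition of study-related agree with section 7.1.3. Add drug withholding and the OGTT to the risks in section 1.3.1, so that the expectedness judgement in section 7.2.3 has a protocol reference. Reconcile the number of MRIs between sections 1.2 and 3.1 and Attachment A on one side and sections 9.3.1 and 12.3 on the other.

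The cost is one more item on the form and some wording. Slightly more events will be counted as study-related. No clinical rule changes.

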## 6.4.4 Post-Exercise Phase Visit

Participants will undergo blood tests, VO2R, and a final MRI to compare with results collected prior to the exercise intervention. The final visit should occur within two weeks after the last exercise session. This will allow for feasible scheduling, data collection, and study completion considerations.

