# 2 Objectives and Purpose

# 2.1 Primary Objective

The primary objective is to assess and compare the interventions (exercise versus control phase) in terms of the baseline to follow-up change in the following outcomes: 1) DTI, plasma ROS level, and the MNSI assessment of DPN symptoms (Aim 1); and 2) leg mitochondrial function, oxidative capacity (31P-MRI), peak MV response (BOLD-MRI), the proportion of fat-free muscle (IDEAL-MRI) and leg muscle strength (Aim 2).

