# 3 Study Design and Endpoints

# 3.1 Description of Study Design

This single-center, longitudinal design study uses multinuclear-MRI to evaluate the mechanistic effects of exercise on skeletal muscle function and peripheral nerve integrity in patients with DPN, and to determine whether exercise can reverse DPN symptoms. Forty DPN patients will be enrolled and be prescribed a 10-week exercise program following a 4-week non-exercise period. The exercise program will comprise aerobic and resistance components; a moderate level of intensity will be calculated based on results from a maximal graded exercise test (VO2R) conducted prior to the intervention. Multinuclear-MRI data will be acquired at baseline, as well as before and after the intervention that can provide mechanistic insight into the adaptations in lower leg muscle function and peripheral nerve integrity of patients with DPN, and their role in improving DPN symptoms.

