## 6.4.2 Maximal Graded Exercise Testing (VO2R Assessment)

Maximal graded exercise testing (VO2R assessment) will be performed prior to the 10-week exercise intervention by an exercise physiologist at Langone Orthopedic Center, [name]. A standardized exercise protocol with a recumbent stepper/treadmill will be used (Trackmaster, USA). We will use a ramping protocol with increases in workload equivalent to 0.5 METS per 1 minute. Continuous monitoring of heart rate will be performed. Additionally, blood pressure and RPE are measured at the end of each stage. Criteria for a "maximal" effort during exercise testing include: reaching a plateau in VO2 with increased workload, a respiratory exchange ratio of greater than or equal to 1.15, a peak HR within 85% of the age-predicted maximal HR (in absence of beta blockage), and an RPE of greater than or equal to 18 (ACSM Guidelines for Exercise Testing and Prescription 10th edition, 2017.) The test will be stopped before maximal effort was achieved if any of the following occur: angina, dyspnea, fatigue (voluntary exhaustion or inability to maintain a speed/cadency of 115 on the stepper), hypertension (250 mm Hg systolic or 115 mm Hg diastolic), and hypotension (>10mmHg drop in blood pressure with workload increase), or ischemic electrocardiographic abnormalities. The same exercise physiologist will administer tests (before and after intervention). In addition to standardized protocols, the following procedures will be used to minimize bias: 1) The use of timed encouragement scripts

2) No review of pre-intervention test results before post intervention tests

CONFIDENTIAL

This material is the property of the NYU School of Medicine and Langone Medical Center. Do not disclose or use except as authorized in writing by the study sponsor

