# Attachment A

# Schedule of Events

Activity	Week 0	Week 1	Week 2	Week 3	Week 4	Week 5	Week 6	Week 7	Week 8	Week 9
Consent		Х								
MNSI	Х	Х								
Medical History	Х									
Height/Weight		Х					Х			
OGTT		Х								
Biweekly Health Assessment				х		Х				
VO 2 R Assessment							Х			
Plantar flexion training		Х								
Bloodwork		Х								
Actigraph**		Х	Х					Х	Х	
MRI		Х				Х				
Aerobic exercise								Х	Х	Х
Resistance exercise								Х	Х	Х
PROMIS								Х		
Calf muscle performance								Х		
9-item physical performance test								Х	Х	Х
Blood Pressure (BP)								Х	Х	Х

\*\*Actigraph to be worn for at least one week.

CONFIDENTIAL This material is the property of the NYU School of Medicine and Langone Medical Center. Do not disclose or use except as authorized in writing by the study sponsor Drug/Device Template Version: 13 JUN 2016

Page 2

# Attachment A Schedule of Events Cont....

Activity	Week 10	Week 11	Week 12	Week 13	Week 14	Week 15	Week 16	Week 17	Week 18
Consent									
MNSI									Х
Medical History									
Height/Weight								Х	
OGTT									Х
Biweekly Health Assessment									
VO 2 R Assessment								Х	
Plantar flexion training									
Bloodwork									Х
Actigraph						Х	Х		
MRI									Х
Aerobic exercise	Х	X	х	Х	х	Х	х		
Resistance exercise	Х	х	х	Х	х	Х	х		
PROMIS							х		
Calf muscle performance							х		
9-item physical performance test	X	X	X	X	X	х	X		
Blood Pressure (BP)	X	Х	Х	Х	Х	Х	х

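### The maximal graded exercise test is scheduled after the pre-exercise MRI but in the week before the final MRI, OGTT and bloods, so any short-term effect of a maximal bout may enter only the follow-up measurements

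*Combined protocol and SAP*

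**What the plan says.** The protocol calls for three scans. Section 3.1 states: "Multinuclear-MRI data will be acquired at baseline, as well as before and after the intervention". The primary objective in section 2.1 is to "assess and compare the interventions (exercise versus control phase) in terms of the baseline to follow-up change".

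Section 6.4.2 says the maximal graded test "will be performed prior to the 10-week exercise intervention by an exercise physiologist", and "The same exercise physiologist will administer tests (before and after intervention"). It sets no position for either test relative to the scans.

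Section 6.4.4 lists blood tests, VO2R, "and a final MRI to compare with results collected prior to the exercise intervention". Its one timing rule is "The final visit should occur within two weeks after the last exercise session". That is an upper limit counted from the last training session. It says nothing about the interval from VO2R to the scan or to the blood draw.

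The order comes from Attachment A, read by column:

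| Activity | Weeks |
|---|---|
| MRI | 1, 5, 18 |
| VO2R test | 6, 17 |
| OGTT and bloodwork | 1, 18 |
| Aerobic and resistance training | 7 to 16 |

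The contents list agrees for the pre-training part: it places the post-non-exercise visit before the graded test. The Attachments page says the attachments are not part of the protocol and are modified separately, so the protocol body itself leaves the order open.

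**The concern.** Section 6.4.2 defines the graded test as maximal effort (a plateau in VO2, respiratory exchange ratio of at least 1.15, RPE of at least 18). The measurements that follow it in Week 18 include PCr resynthesis and BOLD response in the calf, plasma hydrogen peroxide, and insulin sensitivity from the OGTT. The protocol's own rationale is that exercise acts on microvascular dilation, oxidative stress and insulin sensitivity, so a recent maximal bout is a plausible short-term influence on these same quantities.

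The plan already standardises other short-term influences before scans and OGTT: overnight fasting, two days without oral diabetes medication, and no morning insulin. Recent exercise is not standardised in the same way.

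What is at stake is attribution. A transient shift present only at Week 18 would be read as an effect of ten weeks of training, or would offset one. Section 9 specifies no variable, such as days since the test, that could separate the two.

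**Working it through.** **1. Order of events.** Before training, the scan (Week 5) comes before the test (Week 6). After training, the test (Week 17) comes before the scan, OGTT and bloods (Week 18). The number of study VO2R tests before each scan is:

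| Scan | Earlier VO2R tests | Nearest one |
|---|---|---|
| Week 1 | 0 | none |
| Week 5 | 0 | none |
| Week 18 | 2 | Week 17 |

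The Week 6 test lies before the whole training phase, so only the Week 17 test is recent.

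**2. Intervals, from calendar weeks alone.**
- VO2R in Week 17 to scan in Week 18: the last day of one week to the first day of the next is 1 day; first day to last day is 13 days.
- Last training session in Week 16 to scan in Week 18: 8 to 20 days. With the two-week limit of 6.4.4, this becomes 8 to 14 days.
- If the scan were pulled forward into Week 17: 1 to 13 days after the last session.

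**3. Where a shift would go.** Let Y1, Y5 and Y18 be an MRI outcome at the three scans, and let a be a short-term shift present only at Week 18.
- Control-phase change: Y5 − Y1, with no a.
- Exercise-phase change: Y18 − Y5, containing a.
- Exercise minus control: (Y18 − Y5) − (Y5 − Y1), containing the full a.
- Section 9.3.1 describes only enrolment and post-program scans. On that reading the change is Y18 − Y1, which also contains a.
- Bloods and OGTT have no Week 5 draw in Attachment A, so no control-phase change exists. The shift enters the Week 1 to Week 18 change directly.

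**4. The plan's power figure, as a check on the inputs.** Section 9.4 gives 80% power for changes of 10% to 18% of the baseline mean (n = 40, two-sided 5%). The normal approximation is (1.960 + 0.842) × SD / √40, with SDs from Table 4 and baseline means from Table 3:
- BOLD: 2.802 × 1.26 / 6.325 = 0.558; 0.558 / 3.24 = 17.2% (17.7% by noncentral t).
- PCr: 2.802 × 12.85 / 6.325 = 5.692; 5.692 / 41.16 = 13.8% (14.2% by t).
- MNSI: 2.802 × 1.78 / 6.325 = 0.788; 0.788 / 5.2 = 15.2% (15.5% by t).

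These lie inside the stated range, and BOLD reproduces its upper end.

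**5. Sensitivity to an assumed shift.** The shift sizes are assumptions; none comes from the documents. With no training effect, the chance of a significant exercise-phase change in an unweighted paired t-test with n = 40 follows from a noncentral t with 39 degrees of freedom and noncentrality a × √40 / SD. For BOLD at 5% of baseline, a = 0.05 × 3.24 = 0.162 and the noncentrality is 0.162 × 6.325 / 1.26 = 0.81.

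| Assumed shift, % of baseline mean | BOLD | PCr |
|---|---|---|
| 0 | 5% | 5% |
| 2 | 6% | 7% |
| 5 | 13% | 17% |
| 10 | 36% | 51% |

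The first row applies if no effect of the bout survives to the scan.

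**The case against.** The strongest reply is that nothing in the documents shows an after-effect lasting as long as the scheduled gap. At the long end, 13 days, it may well be nil. This stands. A reader might infer that the follow-up data do carry an acute artefact; the documents support only that they may. The table above shows what an assumed shift would do and is not evidence that one exists.

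Four further points limit the concern.

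- **Same-day testing.** A reader might take the single-visit wording of 6.4.4 to mean that the test and the scan fall on one day. Nothing schedules that. Attachment A puts them in different weeks, the test is done at the orthopedic center, and the scan is done fasted at the imaging center. The wording merely does not exclude it.
- **Order within 6.4.4.** The list names bloods before VO2R, so it cannot be used to show that the test precedes the blood draw. The asymmetry rests on Attachment A.
- **Cancellation.** It is tempting to say that no affected outcome cancels against the control phase. That argument holds for MRI outcomes only, because hydrogen peroxide and OGTT have no control-phase change in Attachment A.
- **Training sessions.** A reader might infer that the final scan can directly follow a training session. Section 6.4.4 has no minimum, but Attachment A leaves all of Week 17 free of training, which implies at least about 8 days.

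Scanner availability is also a real constraint: section 4.5 cites it, and 6.4.4 justifies its window by feasible scheduling. None of this explains why the order differs before and after training, or gives a reason to keep the difference.

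**Conclusion.** The point holds as a correctable asymmetry in the schedule. On Attachment A, a recent maximal test precedes only the final MRI, OGTT and bloods, by about 1 to 13 days, and the protocol body sets neither the order nor a minimum interval. If any short-term effect persists to Week 18, all of it enters the exercise-phase change, and for MRI outcomes all of it enters the exercise-minus-control difference.

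Its size, direction and duration cannot be derived from the documents, so it could mimic benefit, mask it, or be absent. The conclusion rests on reading Attachment A by column and on the plausibility of a transient effect on these outcomes. It does not rest on any assumed shift size. The change is worth making because it removes the question at almost no cost.

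**What to change.** In section 6.4.4 and Attachment A, state that the final bloods, OGTT and MRI come before the post-exercise VO2R test, matching the order used before training. Do this by moving VO2R to after the scan. Simply exchanging Weeks 17 and 18 should be avoided: it would bring the scan up against the last training session and could cut that gap from about 8 days to 1.

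In 6.4.4, add a stated minimum interval between the last training session and the scan and bloods, inside the existing two-week limit, so that the separation Attachment A now implies (about 8 days) is secured in the protocol itself. State whether the two-week limit also covers the later VO2R test. Record the days from last session to scan for every participant.

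The cost is a reordering of existing appointments and a few sentences of text, with no added visits. VO2R falls a few days later; it is not among the endpoints listed in section 3.2.1. Scan scheduling becomes slightly tighter.
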